8.2 Concomitant illness and medical history

A **concomitant illness** is any illness that is present at the start of the trial (Visit 1 in this trial).

Medical history is an account of medical events that the subject has experienced in the past, and the disease related to the trial as judged by investigator.

The information collected for concomitant illness should include diagnosis, and date of resolution or continuation. The information collected for medical history should include diagnosis. Any change to a concomitant illness should be recorded during the trial. A clinically significant worsening of a concomitant illness must be reported as an AE.

8.3 Concomitant medication

A **concomitant medication** is any medication, other than the trial products, which is taken during the trial period (including the screening period).

Details of any concomitant medication must be recorded at Visit 1 (screening visit). Any changes in concomitant medication must be recorded at each visit as they occur.

The information collected for each concomitant medication includes trade name or generic name, indication, start date and stop date or continuation.

If a change is due to an AE, then this must be recorded and reported according to section [12](#). If the change influences the subject's eligibility to continue in the trial, the monitor must be informed.

In case of systemic adrenocortical steroid, the information collected for each concomitant medication includes route of administration. If start date is more than one year ago before date of Visit 1, the date of one year ago before Visit 1 can be recorded on the concomitant medication form in the CRF.

Prohibited concomitant medication

Concomitant use of the following drugs, which may effect on growth acceleration, will be prohibited during the trial.

Thyroid hormone (except the replacement treatment), anti-thyroid hormone, androgen, oestrogen, progesterone, anabolic steroid, systemic adrenocortical steroid, derivative of gonadotropin releasing hormone, somatomedin C (IGF-1), and GH preparation except for the trial products.

A use of systemic adrenocortical steroids (hydrocortison \leq 20 mg/day) for less than 13 weeks may be allowed.

8.4 Assessments for efficacy

8.4.1 Height

Height must be measured three times (without shoes and socks) in total at all visits. Subjects should step away from the height measurer between each measurement. Each measurement will be recorded in centimetre in the CRF and recorded to one decimal place.

A height data within the period between 40 and 64 weeks prior to Visit 1 (screening) is used for assessment for efficacy as a control data. The height had been measured during normal management of subjects.

8.5 Assessments for safety

8.5.1 Adverse events

AEs will be recorded at each visit in accordance with the procedures described in section [12.2](#). Any clinically significant worsening since baseline of a previous finding must be reported as an AE. For further information, please refer to section [12](#).

8.5.2 Laboratory assessments for safety

For laboratory analysis of safety parameters, the volumes of blood sampling at each visit are as follows:

- At Visit 1 (screening), Visit 8, Visit 12, Visit 16 and Visit 20, 14.1 mL of blood will be drawn for each visit.
- At Visit 3, Visit 5, Visit 7, Visit 9, Visit 11, Visit 13, Visit 15, Visit 17 and Visit 19, 5.5 mL of blood will be drawn for each visit.
- At Visit 6, Visit 10, Visit 14 and Visit 18, 7.8 mL of blood will be drawn.

The laboratory analyses will be performed by a central laboratory unless otherwise specified. Descriptions of assay methods, laboratory supplies and procedures for obtaining samples, handling and storage of samples and information on who will perform the assessments, will be described in a trial-specific laboratory manual provided by a central laboratory.

Laboratory samples can be drawn at another day than on the day of the actual visit as long as it is within the visit window stated in the flow chart (section [2](#)). For some samples drawn during the trial it is necessary for subjects to visit in fasting state for the sensitivity of the analysis.

The samples will be coded in order to keep subject identity anonymous.

Laboratory printouts except IGF-I will be sent by the central laboratory to the investigator on an on-going basis. All laboratory printouts must be dated and signed by the investigator on the day of evaluation. If a result is outside the normal range, the investigator must judge whether the abnormality is clinically significant. If considered clinically significant the result must be reported as an AE according to section [12](#).

If any clinically significant abnormalities occur at Visit 1, this must be recorded on the medical history/concomitant illness form. In the case of any clinical significant worsening since Visit 1 the investigator must comment in the medical record and the change must be reported as an AE according to section [12](#).

Laboratory printouts of IGF-I will be sent by the central laboratory to the investigator after the database lock of the extension phase (hereinafter referred to as 2nd database lock) in this trial to maintain double-blind design in this trial. All the laboratory printouts of IGF-I must be dated and signed by the investigator on the day of evaluation.

Laboratory results of IGF-I of the pivotal phase will be transferred to the sponsor directly for the data management and the analysis after the database lock of the pivotal phase (hereinafter referred to as 1st database lock) to submit the analysis results to the authority.

All laboratory data will be transferred electronically from the central laboratory to the sponsor .

8.5.2.1 Haematology

At Visits 1, 3, 5, 6, 7, 8, 9, 10, 11, 12, 13, 14, 15, 16, 17, 18, 19 and 20, blood samples will be drawn for the measurement of the following:

- RBC
- WBC
- Haemoglobin
- Haematocrit
- Platelets
- Leukocyte fractions (neutrophil leukocyte, lymphocyte, monocyte, eosinophil leukocyte and basophilic leukocyte)

8.5.2.2 Biochemistry

At Visits 1, 3, 5, 6, 7, 8, 9, 10, 11, 12, 13, 14, 15, 16, 17, 18, 19 and 20, blood samples will be drawn for the measurement of the following:

- Aspartate aminotransferase (ASAT/SGOT)
- Alanine aminotransferase (ALAT/SGPT)
- γ -glutamyl transpeptidase (γ -GTP)
- Alkaline phosphatase (ALP)
- Total protein
- Blood urea nitrogen (urea) (BUN)
- Creatinine
- Sodium (Na)
- Potassium (K)
- Chloride (Cl)
- Calcium (Ca)
- Phosphorus (P)

8.5.2.3 Bone metabolism marker

At Visits 1, 6, 8, 10, 12, 14, 16, 18, and 20, blood samples will be drawn for the measurement of the following:

- Bone-alkaline phosphatase (BAP)
- Osteocalcin

8.5.2.4 Lipid

At Visits 1, 3, 5, 6, 7, 8, 9, 10, 11, 12, 13, 14, 15, 16, 17, 18, 19 and 20 the final visit, blood samples will be drawn for the measurement of the following:

- Total-cholesterol
- LDL-cholesterol
- HDL-cholesterol

8.5.2.5 Endocrinology

At Visits 1, 3, 5, 6, 7, 8, 9, 10, 11, 12, 13, 14, 15, 16, 17, 18, 19 and 20, blood samples will be drawn for the measurement of the following:

- Thyroid-stimulating hormone (TSH)
- Free thyroxine (FT₄)
- Free triiodothyronine (FT₃)

8.5.2.6 IGF-I

At Visits 1, 3, 5, 6, 7, 8, 9, 10, 11, 12, 13, 14, 15, 16, 17, 18, 19 and 20, blood samples will be drawn for the measurement of IGF-I.

8.5.2.7 Blood coagulation tests

At Visits 1, 6, 8, 10, 12, 14, 16, 18 and 20, blood samples will be drawn for the measurement of the following:

- Prothrombin time
- Partial thromboplastin time

8.5.2.8 Urine samples

At Visits 1, 3, 5, 6, 7, 8, 9, 10, 11, 12, 13, 14, 15, 16, 17, 18, 19 and 20, urine samples will be drawn for the measurement of the following:

- Protein
- Glucose
- Occult blood

8.5.2.9 OGTT

The OGTT will be performed at Visit 1, 8, 12, 16 and 20. At Visit 1, the OGTT will be performed between Visit 1 and ending the time the subjects are registered (just before Visit 2). After having fasted apart from water from 9 pm in the previous night, the OGTT will be conducted.

1.75 g/kg body weight (maximum: 75 g) glucose will be administered orally after taking blood sample. Blood samples for glucose and insulin will be collected at 30, 60, 90, and 120 min after administration.

The investigator will judge based on the OGTT results whether the subjects are diabetic type or normal type or borderline type according to the classification and diagnosis of diabetes mellitus¹⁹ at Visit 1. The eligibility of the subjects (exclusion criterion 3 [children with diabetic type]) must be confirmed (section [6.3](#)), and recorded in the CRF.

8.5.2.10 HbA_{1c}

At Visits 1, 6, 8, 10, 12, 14, 16, 18, and 20, blood samples will be drawn for the measurement of HbA_{1c}.

8.5.3 Vital signs

At each visit, diastolic blood pressure, systolic blood pressure and pulse will be measured after a 5-minute rest in a sitting position.

Any changes in subsequent visits as compared to Visit 1 which fulfil the criteria for an AE must be recorded as an AE.

8.5.4 ECG

A 12-lead ECG will be recorded after a 3-minute rest in a supine position at Visits 1, 6, 8, 10, 12, 14, 16, 18 and 20. The ECG reader will compute the PR, QT and QTc intervals (QT intervals corrected for heart rate), QRS duration, and RR interval and heart rate. The PR, QT and QTc intervals, QRS duration, and RR interval and heart rate will be recorded in the CRF.

At Visit 1, the investigator will evaluate the findings from the 12-lead ECG examination and classify it as either 'normal', 'abnormal, not clinically significant' or 'abnormal, clinically significant' in the CRFs. An 'abnormal, clinically significant' finding at Visit 1 will be recorded as a concomitant illness.

At the subsequent visits, any clinically significant worsening of a pre-existing condition as well as any new clinically significant finding will be recorded in the CRF as an AE (section [12](#)).

Absolute QTc prolongation defined as QTc > 450 ms will be reported as "abnormal, clinical significant" referring to the ICH E14 guideline²².

In case of "abnormal" ECG, the investigator must comment in the medical record.

If the ECG is performed before the subject has signed the informed consent form, it must be documented in the medical record that performing the procedure was not related to this trial.

8.5.5 Transthoracic echocardiography

A transthoracic echocardiography (TTE) will be performed at Visits 1, 6, 8, 10, 12, 14, 16, 18 and 20.

At Visit 1, the investigator will evaluate the findings from the TTE examination (morphology and dynamic parameters) and classify it as either 'normal', 'abnormal, not clinically significant' or 'abnormal, clinically significant' in the CRFs. An 'abnormal, clinically significant' finding at Visit 1 will be recorded as a concomitant illness. Morphology parameters are LV diastolic dimension, LV systolic dimension, interventricular septum, LV posterior wall, LVOT diameter, left atrium, left atrial area, left atrial volume and RV diastolic dimension. Dynamic parameters are cardiac output, ejection fraction and diastolic function. At the subsequent visits, any clinically significant worsening of a pre-existing condition as well as any new clinically significant finding will be recorded in the CRF as an AE (section [12](#)).

In case of "abnormal" TTE, the investigator must comment in the medical record.

If the TTE is performed before the subject has signed the informed consent form, it must be documented in the medical record that performing the procedure was not related to this trial.

8.5.6 Bone age

X-ray picture of carpal bones of left hand will be taken for bone age determination at individual site at Visit 2, 8, 12, 16 and 20. Centralised evaluation of bone age will be done by RUS score method of Tanner-Whitehouse II (TW2) method. Bone age is a first decimal figure.

The analysis result sheet will be obtained from the responsible person of bone age determination. Bone age will be recorded in the CRF.

8.6 Other assessments

8.6.1 Pubertal sign

Pubertal signs will be assessed at all visits. Boys will be observed by pubes and penis according to the method of Tanner¹⁸ (Tanner stages I to V) and testicular volume using an orchidometer²³. Testicular volume is basically an integer number. In case the measured value is medium, it is recorded in CRFs as a first decimal figure. Girls will be also observed by pubes and breast according to the method of Tanner¹⁸ (Tanner stages I to V) and menses.

Prepubertal children are defined as the result corresponds to all of the following items:

- All of Tanner parameters = stage I
- testicular volume < 4 mL (for boy subjects only)
- none of menses (for girl subjects only)

The investigator will judge whether the subjects are prepubertal children according to the above definition at Visit 1. The eligibility of the subjects (inclusion criterion 6 [prepubertal children]) must be confirmed (section [6.2](#)), and recorded in the CRF.

8.6.2 Body weight

Body weight will be measured (without coat and shoes) and recorded in the CRF at all visits. When body weight is measured with a second decimal figure, the second below decimal figure is rounded up or down to the nearest first decimal.

8.7 Subject compliance

At each visit the investigator will emphasise the necessity for the subject to adhere to trial procedures in order to encourage subject compliance.

Subjects will be asked to record compliance with trial products in the daily dosage note and instructed to be checked it by the investigator at the next visit.

If a subject is discovered to be non-compliant, the investigator must inform the subject of the importance of taking trial products as directed.

9 Trial supplies

Trial supplies comprise the trial products and auxiliary supplies.

9.1 Trial products

The trial products during the treatment will be as follows:

- NN-220 (somatropin [genetical recombination]) 5 mg/1.5 mL pre-filled pen for 5 mg
- NN-220 (somatropin [genetical recombination]) 10 mg/1.5 mL pre-filled pen for 5 mg

Both the trial products cannot be distinguished from one another.

Please refer to the TMM provided by Novo Nordisk A/S for details regarding trial products.

Novo Nordisk A/S, Denmark, will provide the trial products and the sponsor (Novo Nordisk Pharma Ltd.) will supply them.

9.2 Packaging and labelling of trial products

Trial products will be packaged and labelled by Novo Nordisk A/S, Denmark.

Labelling will be in accordance with Annex 13²⁴, local law and trial requirements.

Please refer to the TMM provided by Novo Nordisk A/S for details regarding trials products packages.

The investigator will provide each subject with the directions for use (DFU) for NN-220 pre-filled pen.

9.3 Storage, handling, accountability and destruction of trial products

9.3.1 Storage and handling

Storage conditions for NN-220:

- Before use: store in a refrigerator at 2°C to 8°C in the outer carton to protect from light and do not freeze
- Do not store the product directly adjacent to the refrigerator cooling element
- Do not use the product if it has been frozen
- Keep the product away from direct light
- Remove the needle and put the pen cap back on when the pen is not in use
- Do not use the product after the expiration date printed the outer carton and pen

In use time NN-220 may be stored for a maximum of 35 days in a refrigerator. Do not freeze.

Please refer to the TMM provided by Novo Nordisk A/S for further details regarding handling of trial products at sites.

The temperatures during storage should be monitored by a calibrated, stationary and continuously recording system. Minimum requirement is a calibrated minimum/maximum thermometer. The measuring device can be either mechanic or electronic. A temperature log must be kept to document storage within the right temperature interval. The temperature reading must be transferred to the temperature log every working day. Storage facilities should be checked frequently (at least once every working day).

The investigator must ensure the availability of proper storage conditions, and record and evaluate the temperature. The investigator must inform Novo Nordisk immediately if any trial product has been stored outside defined conditions (e.g., outside temperature range)

Returned trial products (used, partly used or unused including empty packaging material) must be stored separately from non-allocated trial products.

The IV/WRS will assign the subject to one of the two treatments groups before the procedures at Visit 2.

NN-220

The correct dispensing unit numbers (DUN) must be dispensed to the subject. The investigator must not dispense trial products to any person not included in the trial.

9.3.2 Drug accountability and destruction of trial products

The responsibility for storage and drug accountability of the trial products at the trial site rests with the head of the trial site. The head of the trial site should assign some or all of the responsibilities for accountability of the trial products at the sites to a trial product storage manager (a pharmacist in principle). The trial product storage manager should control and take accountability of the trial products in accordance with procedures specified by the sponsor. The head of the trial site or the trial product storage manager must ensure the availability of proper storage conditions, and record and evaluate the temperature.

Destruction must not take place until drug accountability has been reconciled by Novo Nordisk. Destruction will be done according to local procedures. Destruction of products must be documented.

The investigator or delegated person will perform drug accountability of trial products using the IV/WRS drug accountability module. The subjects are instructed to return all used, partly used and unused trial products at the next visit. Please refer to the flow chart (section [2](#)).

The monitor will reconcile the drug accountability of trial products using the IV/WRS drug accountability module.

The destruction of trial products will be recorded on a destruction form, which will be signed by the person responsible for the destruction.

9.4 Auxiliary supply

The following will be supplied by Novo Nordisk Pharma Ltd.

- FlexPro[®] PenMate[®] injection supportive device
- PenNeedle[®]
- Other relevant materials required for the trial such as needle containers for used needles and antiseptic cotton

Protocol
Trial ID: GHLIQUID-4020
UTN: U1111-1131-5892

~~CONFIDENTIAL~~

Date: 21 March 2013
Version: 1.0
Status: Final
Page: 50 of 87

Novo Nordisk

At all times during the trial, only DUNs allocated by the IV/WRS are allowed to be dispensed to a subject. By doing this it will be ensured that:

- needed stock is available at a site for the subjects
- no allocation of trial product that will expire before the next dispensing contact
- drug accountability can be made in IV/WRS

If a subject needs trial product between dispensing visits, the investigator must make an additional dispensing.

The IV/WRS user manual will be provided to each trial site.

11 Randomisation procedure and breaking of blinded codes

11.1 Randomisation

All subjects will be randomised to one of the two groups (0.033 mg/kg/day or 0.066 mg/kg/day) before procedures at Visit 2. The randomisation will be carried out in a 1:1 manner (0.033 mg/kg/day: 0.066 mg/kg/day) using the IV/WRS.

The trial sites should dispense trial products allocated by the IV/WRS in order to:

- secure available stock at site to cover the drug supply needed for the enrolled subjects
- ensure that no subjects are provided with trial products that will expire in between dispensing visits
- ensure that it will be possible to perform drug accountability of trial products by using the IV/WRS

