17.1 Sample size calculation

The primary endpoint is change in height SDS from baseline to 104 weeks of treatment¹⁷. Since the primary objective of this trial is to evaluate the growth promoting effect of NN-220, the following hypothesis will be statistically tested; $H_0: \mu_1 = \mu_2$ vs. $H_1: \mu_1 \neq \mu_2$, where μ_i is the population mean, i

=1, 2 represents the 0.033 mg/kg/day and 0.066 mg/kg/day, respectively. Primary analysis for primary endpoint will be performed based on the analysis of covariance (ANCOVA) model with treatment as a fixed effect and baseline height SDS as a covariate.

The sample size is calculated using two sided two sample t-test for $\mu_1 = \mu_2$ with a 5% significance level.

According to Osio D., et al. (2005)⁷, the mean (SD) of change in height SDS of treatment with 0.033 mg/kg/day and 0.066 mg/kg/day from baseline was 0.8 (0.4) after 1 year and a further mean gain of 0.4 (0.7) was observed after 2 years (mean and SD for each treatment are not presented in the article). In the GHLiquid-1516 trial (Japanese subjects with short stature born small for gestational age), mean difference of height SDS between 0.033 mg/kg/day and 0.067 mg/kg/day was 0.6 at 104 weeks. The results of the sample size calculations with power 80% can be seen in [Table 17-1](#) for different SDs and mean treatment differences that can be detected.

Table 17-1 Sample size per treatment group with power 80%

		Mean difference of 0.033 mg/kg/day and 0.066 mg/kg/day					
SD	0.35	0.40	0.45	0.50	0.55	0.60	
0.40	22	17	14	12	10	9	
0.45	27	21	17	14	12	10	
0.50	34	26	21	17	15	12	
0.55	40	31	25	21	17	15	
0.60	48	37	29	24	20	17	

With mean difference $\mu_2 - \mu_1 = 0.45$ and $SD = 0.5$, 21 subjects per treatment group give power 80%. In the GHLiquid-1516 trial, withdrawal rates were 6.1% and 5.9% for 0.033 mg/kg/day and 0.067 mg/kg/day, respectively. Assuming 10% of withdrawal rate from this result, sample size was determined as 24 per treatment group in order to ensure the power on PP analysis set. Thus, the sample size of 48 subjects in total is set, assuming exclusion of 6 subjects from PP analysis set.

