2.3 Primary endpoint

The primary endpoint is change in height SDS from baseline to 104 weeks of treatment according to the Japanese reference dataⁱⁱ. A height SDS will be also calculated according to the Noonan syndrome reference data in Japaneseⁱⁱⁱ.

Statistical analysis

Since the primary objective of this trial is to evaluate the growth promoting effect of NN-220, the following hypothesis will be statistically tested; $H_0: \mu_1 = \mu_2$ vs. $H_1: \mu_1 \neq \mu_2$, where μ_i is the population mean, $i = 1, 2$ represents 0.033 mg/kg/day and 0.066 mg/kg/day, respectively. Primary analysis for the primary endpoint will be performed based on the ANCOVA model with treatment as a fixed effect and baseline height SDS as a covariate.

Sensitivity analysis

The same analysis as for the primary endpoint will be repeated on the PP analysis set.

All height SDS measurements at scheduled time points after randomisation will be analysed in a linear mixed model with treatment, time and interaction between treatment and time as fixed effects, baseline height SDS and interaction between baseline and time as a covariate and subject as a random effect. This approach assumes that data are missing at random according to the taxonomy defined by Rubin (1976)^{iv}. Treatment differences at 104 weeks will be estimated using this model.

Any marked difference concerning treatment differences between the sensitivity results and the result from the primary endpoint will be commented upon in the CTR.

Exploratory analysis

In order to investigate effects of sex, age at start of treatment and baseline height SDS on the primary endpoint, change in height SDS from baseline to 104 weeks of treatment will be analysed based on the ANCOVA model with treatment and sex as fixed effects and age at start of treatment and baseline height SDS as covariates. Parameter estimates for sex, age at start of treatment and baseline height SDS will be presented together with two-sided 95% CIs and p values.

Height SDS (Noonan syndrome reference data in Japanese)

In addition to height SDS according to the Japanese reference data, height SDS will be also calculated according to the Noonan syndrome reference data in Japanese. The change in height SDS (Noonan syndrome reference data in Japanese) from baseline to 104 weeks of treatment will be

analysed based on the ANCOVA model with treatment as a fixed effect and baseline height SDS (Noonan syndrome reference data in Japanese) as a covariate.

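### The primary ANCOVA leaves out age at start of treatment; adding it before database lock is a cheap safeguard for the dose contrast, with a modest gain that depends on how prognostic age is.

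*Protocol*

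**What the plan says.** - **Allocation.** Protocol 11.1: "The randomisation will be carried out in a 1:1 manner (0.033 mg/kg/day: 0.066 mg/kg/day) using the IV/WRS". It names no stratification or minimisation factor. Part of Protocol section 10 (IV/WRS) is not in the supplied text, so a factor described there cannot be fully excluded.
- **Age range.** Protocol 6.2, criterion 4, admits boys from 3 to under 11 years and girls from 3 to under 10.
- **Primary model.** SAP 2.3 specifies an "ANCOVA model with treatment as a fixed effect and baseline height SDS as a covariate". Protocol 17.1 and 17.3 give the same model. The mixed-model sensitivity analysis also contains neither age nor sex.
- **Exploratory model.** SAP 2.3 adds a second ANCOVA "In order to investigate effects of sex, age at start of treatment and baseline height SDS on the primary endpoint". It has treatment and sex as fixed effects, with age and baseline height SDS as covariates. The outputs listed for it are the estimates for sex, age and baseline height SDS; the treatment difference is not among them.
- **Sample size.** Protocol 17.1: "The sample size is calculated using two sided two sample t-test", "with a 5% significance level". The chosen case is a difference of 0.45 with SD 0.5, giving 21 per group for 80% power. Then: "Assuming 10% of withdrawal rate from this result, sample size was determined as 24 per treatment group", and "Thus, the sample size of 48 subjects in total is set, assuming exclusion of 6 subjects from PP analysis set".

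**The concern.** Age at start of treatment is known for every child at randomisation, and the SAP itself picks it out as something that may influence the primary endpoint. The protocol also limits entry age because efficacy is hard to judge once puberty has begun. Yet the confirmatory model ignores age, and no balancing by age is described.

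Two things follow if age is prognostic given baseline height SDS. The variance that age explains stays in the error term, so the confidence interval for the dose difference is wider than it need be. And if the arms happen to differ in mean age, part of the observed dose difference reflects age. The listed outputs would not show whether the dose contrast survives adjustment, and choosing covariates after unblinding would carry less weight.

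**Working it through.** **1. The plan's own figure.** For a two-sided two-sample t-test, the noncentrality is (0.45/0.5) × √(n/2) with 2n − 2 degrees of freedom. At n = 21 the exact power is 81.2%, and 21 is the smallest n that reaches 80%. All 30 cells of Table 17-1 reproduce. Withdrawal: 21/0.9 = 23.3, rounded up to 24 per group, 48 in total. The plan's arithmetic is sound.

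**2. Which n applies.** The primary analysis uses the full analysis set with missing height carried forward (SAP 2 and 2.2), so 24 per arm is the main basis. The figure of 21 is the per-protocol allowance.

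**3. Adding age.** Let R² be the share of residual variance that age explains after treatment and baseline height SDS. I take SD 0.5 as the residual SD without age. Adding age:
- multiplies the variance of the treatment difference by (1 − R²);
- multiplies it again by 1 + 1/(2n − 4), the expected cost of chance age imbalance;
- uses one degree of freedom (2n − 3).

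The noncentrality becomes 0.9 × √(n/2) / √[(1 − R²)(1 + 1/(2n − 4))]. R² is not in the documents; the values below are assumptions.

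| Per arm | Without age | R² = 0 | 0.05 | 0.10 | 0.20 |
|---|---|---|---|---|---|
| 24 | 86.3% | 85.5% | 87.2% | 88.9% | 92.1% |
| 21 | 81.2% | 80.2% | 82.1% | 84.1% | 88.1% |

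Break-even is R² of about 0.02 (r about 0.15) at 24 per arm, and slightly higher at 21.

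**4. Adding age and sex.** With two terms, 2n − 4 degrees of freedom, variance factor 1 + 2/(2n − 5), and R² now for both together, power at 24 per arm is 84.6%, 86.4%, 88.1% and 91.5% for the same R². Break-even rises to about 0.05.

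**5. Chance imbalance in age at 24 per arm.** The standard error of the difference in mean age is √(2/24) = 0.289 SD of age, so the 95% range is 1.96 × 0.289 = ±0.57 SD. The chance of a difference above 0.3 SD is about 30%, and above 0.5 SD about 8%. If the SD of age is 2.2 years (an assumption, near a uniform spread over the entry range), the standard error is 2.2 × 0.289 = 0.635 years, the 95% range is ±1.24 years, and the chance of more than one year is about 11%.

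The corresponding 95% range of the shift in the unadjusted dose difference is 0.566 × √R² × 0.5:
- R² = 0.05: 0.566 × 0.224 × 0.5 = ±0.06 SDS
- R² = 0.10: 0.566 × 0.316 × 0.5 = ±0.09 SDS
- R² = 0.20: 0.566 × 0.447 × 0.5 = ±0.13 SDS

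The planned difference is 0.45.

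**6. Check by simulation** (10,000 trials per case for power, 5,000 for type I error; 24 per arm; baseline height SDS in both models). Power without and with age was 85.3% and 84.4% at r = 0, 85.3% and 87.6% at r = 0.3, and 85.1% and 92.6% at r = 0.5. These runs also pay for the baseline covariate, so they sit up to about 1 point below the formula. Across both sample sizes, type I error was 4.8% to 5.5% with or without age.

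**The case against.** The case for leaving the model alone has weight.

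- **No evidence that age is prognostic here.** The endpoint is already standardised to reference data, all children are prepubertal at entry, and baseline height SDS is in the model. Protocol 6.2 puts mean onset of puberty at 13.5 to 14.5 years in boys and 13 to 14 in girls, beyond the age that most would reach by week 104. Planning to investigate an effect is not evidence of one. This stands, and is why the result is given as a range.
- **Adjustment is not free.** A reader might infer that adding baseline covariates can only help. It cannot: if age explains nothing, power falls by about 1 point, or about 2 with sex as well.
- **No validity problem.** A reader might infer that the dose comparison is biased, or that large age differences are to be expected. Randomisation protects the test, type I error stays near 5%, and a difference above one year has a probability of only about 11% under the assumed SD.
- **The adjusted model already exists.** SAP section 2 promises treatment differences with confidence intervals for all endpoints analysed statistically, which arguably covers the exploratory model. But SAP 2.3 lists that model's outputs and leaves the treatment difference out, so the SAP should say plainly that it will be reported.
- **Stratification.** A reader might infer that allocation should be stratified by age. Protocol section 7 planned the last first visit for December 2014, and the SAP follows a protocol version of March 2016, so this is moot and I do not propose it.

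**Conclusion.** The point holds as a low-cost improvement, not as an error. The primary model is consistent between protocol and SAP, and its 80% power claim reproduces without any reference to age. What the plan lacks is a confirmatory estimate protected against chance age imbalance, or at least an explicit commitment to report an adjusted one.

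At 24 per arm, adding age changes power by about −1 point (R² = 0) to +6 points (R² = 0.20), and helps once R² exceeds about 0.02. This rests on an assumed R², on SD 0.5 being the residual SD without age, and on a linear age effect that is the same in both arms. How much precision the current model gives up, if any, cannot be settled from the documents.

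**What to change.** Before database lock and unblinding:

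1. In SAP 2.3 and Protocol 17.3, define the primary ANCOVA with treatment as a fixed effect and both baseline height SDS and age at start of treatment as covariates.
2. Keep the current model, without age, as a pre-specified sensitivity analysis.
3. Add the treatment difference and its 95% CI to the listed outputs of the existing exploratory model with age and sex.
4. Record the change in SAP section 3.

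The cost is wording, one degree of freedom, and up to about 1 point of power if age is not prognostic. Putting sex in the primary model as well would raise that to about 2 points, so I would leave sex in the exploratory model. If the first database lock has already passed, the primary model should stand; item 3 can still be done, labelled as supportive.
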